### **9.2.7 Important Protocol Deviations**

Important protocol deviations (IPD) are a subset of protocol deviations that may significantly impact the completeness, accuracy, and/or reliability of the study data or that may significantly affect a subject's rights, safety, or well-being. IPD rules will be developed and finalized before database lock.

The protocol deviations that should be considered as potential IPDs include, but are not limited to:

- Violation of subjects rights, safety or well-being
- Subject entered the study despite violation of any inclusion or exclusion criteria
- Subject was less than 80% compliant with study medications
- Subject received excluded concomitant medications
- Subject received the wrong treatment or incorrect doses
- Subject remained in study despite meeting withdrawal criteria

Occurrence of any of these events should be considered as potential IPDs, but the blinded team should categorize them as IPDs only if they have the potential to affect interpretation of study results.

IPDs (from the clinical database or from the site deviation log) will be summarized descriptively based on the FAS and presented by treatment sequence. Additionally, IPDs will

be provided as a subject data listing. No subjects with IPDs will be excluded from any analysis.

### **9.3 Efficacy Analysis**

The primary efficacy objective of this study is to evaluate the efficacy of VX-371+ HS versus HS alone. For efficacy analysis, the statistical inference will be based on change from study baseline. Unless otherwise defined, all efficacy analyses described in this section will be based on FAS. The efficacy analyses will be performed according to the treatment to which the subject was assigned in each period. Data for a period will be used provided that the subject received at least one dose of study drug in that treatment period.

#### **9.3.1 Analysis of Primary Efficacy Endpoint**

##### **9.3.1.1 Definition of Primary Efficacy Endpoint**

[figure not shown]
The primary efficacy endpoint is the absolute change in ppFEV1 from study baseline at Day 28 in each treatment period. ppFEV1 is the ratio of FEV1 (L) to the predicted FEV1 (L), expressed as a percentage. The predicted FEV1 will be calculated according to the Global Lung Initiative (GLI) method. The analysis will include all available measurements up to Day 28 during each treatment period, both on-treatment measurements and measurements after treatment discontinuation.

##### **9.3.1.2 Primary Analysis of Primary Efficacy Endpoint**

The null hypothesis to be tested is that the mean change from study baseline in ppFEV1 at Day 28 is the same for VX-371 with HS versus HS alone.

[figure not shown]
The primary analysis of the primary efficacy endpoint will be based on a mixed-effects model. This model will include the absolute change from study baseline in ppFEV1 at Day 28 as the dependent variable and the following fixed effects: treatment, period and ppFEV1 at study baseline and subject as a random effect. The within-subject covariance will be assumed to have the compound symmetry (CS) structure. Denominator degrees of freedom for the F-test for fixed effects will be estimated using the Kenward-Roger approximation.

[figure not shown]
No imputation of missing data will be performed. Subjects who have data only for one of the periods will have a data structure similar to a parallel-group trial. Assuming that these subjects have dropped out at random, an estimate of treatment effect based on such subjects will be combined with the estimate from subjects who have data in both treatment periods with weights based on the precision of these estimates.

[figure not shown]

[figure not shown]
where “primary efficacy endpoint” is the absolute change from study baseline in ppFEV1 at day 28.

[figure not shown]
Descriptive summary statistics including n, mean, SD, and least-square means (LS means), along with its SE, 95% CI and the within-treatment 2-sided *P* value will be provided by treatment group. The between-treatment LS mean differences [VX-371 + HS versus HS, VX-371 + HS versus VX-371 + placebo, VX-371 + HS versus placebo, and VX-371 + placebo versus placebo] with the corresponding SE, 95% CIs and 2-sided *P* values will be presented. The cumulative distribution of the absolute change from study baseline in ppFEV1 at Day 28 will be plotted by treatment group.

[figure not shown]

[figure not shown]

[figure not shown]

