### **10.3 Method of Assigning Subjects to Treatment Groups**

Approximately 150 subjects will be randomized to 1 of 4 treatment sequences when they are determined to have met all eligibility criteria. Subjects will be randomized in a 2:2:1:1 ratio (VX-371 + 4.2% HS versus 4.2% HS; 4.2% HS versus VX-371 + 4.2% HS; VX-371 + placebo versus placebo; placebo versus VX-371 + placebo), stratifying for ppFEV1 severity (<70% or ≥70%).

Randomization must only occur after all inclusion and exclusion criteria are met and before the first dose of inhaled study drug.

An interactive web response system (IWRS) will be used to assign subjects to treatment sequence. Detailed instructions for randomization will be provided separately.

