## 7.3 Randomization

Approximately 150 subjects will be randomized to 1 of 4 treatment sequences when they are determined to have met all eligibility criteria. Subjects will be randomized in a 2:2:1:1 ratio (VX-371 + 4.2% HS followed by 4.2% HS; 4.2% HS followed by VX-371 + 4.2% HS; VX-371 + placebo followed by placebo; placebo followed by VX-371 + placebo), stratifying by ppFEV1 severity (<70 or  $\geq$ 70).

The 4 treatment sequences are provided in [Table 7-1](#).

An interactive web response system (IWRS) will be used for randomization following a list of randomization codes generated by a designated vendor (Cytel, Inc.).

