### 9.2.1 Subject Disposition

The number of subjects in the run-in period who were not randomized or dosed with the inhaled study drug screen failures during the Run-in Period, number of subjects randomized or dosed with inhaled study drug, and the total number of subjects will be tabulated for the following groups and overall based on their Orkambi and HS status at Screening:

- Orkambi+/HS-
- Orkambi-/HS-
- Orkambi+/HS+
- Orkambi-/HS+

The number of subjects in the following categories will be summarized by treatment group:

- All Subjects Set (Randomized or dosed with Inhaled Study Drug)
- Randomized
- Randomized but never dosed
- Full Analysis Set (FAS)
- Safety Set

The number of subjects in the following categories will be presented by treatment group for each period (Period 1 and Period 2):

- FAS
- Safety Set

The number and percentage (based on Safety Set) of subjects in each of the following disposition categories will be presented by treatment group for each period (Period 1 and Period 2):

- Completed treatment regimen
- Prematurely discontinued the treatment regimen and the reasons for discontinuations
- Prematurely discontinued inhaled study drug and the reasons for discontinuations

- Prematurely discontinued orkambi and the reasons for discontinuations
- Prematurely discontinued the study and the reasons for discontinuations

The number and percentage (based on the overall Safety Set) of subjects in each of the following disposition categories will be presented by treatment group:

- Completed treatment regimen in both periods
- Completed study

A listing will be provided for subjects who discontinued treatment or who discontinued study, along with reasons for discontinuations.

The number and percentage of randomized subjects will be summarized by stratification factor (ppFEV1 at screening), by country and by site, using the number of subjects being randomized in each treatment sequence as the denominator. A randomization listing ordered by randomization date also will be provided.

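### The model leaves out the screening ppFEV1 stratum used in randomisation; this slightly overstates the reported SEs of two between-subject secondary contrasts and the within-treatment means

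*SAP*

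**What the plan says.** SAP 7.3 states "Subjects will be randomized in a 2:2:1:1 ratio" across the four sequences, and Protocol 10.3 adds "stratifying for ppFEV 1 severity (<70% or ≥70"%). SAP 9.2.1 identifies the visit: subjects "will be summarized by stratification factor (ppFEV 1 at screening), by country and by site".

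SAP 9.3.1.2 models the change in ppFEV1 at Day 28 "as the dependent variable and the following fixed effects: treatment, period and" ppFEV1 "at study baseline and subject as a random effect". It adds: "The within-subject covariance will be assumed to have the compound symmetry (CS) structure". Protocol 12.3.3.1 lists the same fixed effects. The stratum appears in neither list, and no reason is given for leaving it out.

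Besides the primary contrast, the same model yields "VX-371 + HS versus VX-371 + placebo, VX-371 + HS versus placebo, and VX-371 + placebo versus placebo", and a two-sided P value for each treatment's own mean change.

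**The concern.** A factor that restricts the randomisation is normally carried into the analysis, so that the reported SE reflects the balance the design has secured.

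Not every output is exposed. By SAP Table 7-1, a subject receives either the two HS treatments or the two 0.17% saline treatments. VX-371 + HS versus HS and VX-371 + placebo versus placebo are therefore within-subject contrasts, and a term that is constant within a subject cancels in anyone with both periods. VX-371 + HS versus placebo and VX-371 + HS versus VX-371 + placebo compare different subjects. They serve two of the three secondary efficacy objectives. The within-treatment means also carry between-subject variance.

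The stratum does not simply repeat the covariate. Screening precedes Day 1 by up to 28 days, or falls on Day -56 to Day -29 for subjects with a Run-in Period. During the Run-in, subjects start Orkambi, stop HS, or both (Protocol Table 8-2). Screening spirometry may be pre- or post-bronchodilator, while predose spirometry at later visits should be pre-bronchodilator (Protocol 11.5.1). SAP 9.2.2 tabulates screening and study-baseline ppFEV1 separately. A second reading can say something about a subject's level that one Day 1 value does not.

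**Working it through.** **1. Reproducing the plan's power (SAP 7.2).** Inputs: SD 7, difference 3, two-sided 0.05, 50 per HS sequence, 10% dropout, so 90 evaluable HS subjects.
- Primary contrast, taking within-subject correlation 0: SD of the difference = 7 × √2 = 9.90; SE = 9.90/√90 = 1.043; t-test on 88 df gives 81.2% power (plan: about 81%).
- Within-treatment, VX-371 + placebo: 45 evaluable of 50; SE = 7/√45 = 1.043; one-sample t-test gives 80.3% (plan: about 80%).

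Both figures reproduce with no stratum or covariate effect.

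**2. How a stratum term enters.** Each subject contributes one Day 28 value per treatment. With 90 HS and 45 saline subjects, the SE of a between-subject contrast is

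SE = √[49 × (1 − ρr) × (1/90 + 1/45)]

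where ρ is the within-subject correlation and r is the share of between-subject residual variance that the stratum explains after study baseline. The product ρr is the proportional cut in total residual variance. The documents state no power for these contrasts, so a 3-point difference is assumed.

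| ρ | r | Variance cut ρr | SE | Power, between-subject contrast | Power, VX-371 + placebo mean |
|---|---|---|---|---|---|
| any | 0 | 0 | 1.278 | 64.4% | 80.3% |
| 0.5 | 2% | 1% | 1.272 | 64.9% | 80.7% |
| 0.5 | 5% | 2.5% | 1.262 | 65.5% | 81.3% |
| 0.5 | 10% | 5% | 1.246 | 66.7% | 82.2% |
| 0.7 | 10% | 7% | 1.232 | 67.6% | 83.0% |

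At ρ = 0 nothing is gained whatever r is.

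**3. How large the cut could be.** The documents do not give the needed quantities, so they are assumed. The true ppFEV1 level has SD 12 to 14, and screening values are restricted to 40 to <90. Screening, Day 1 and Day 28 readings differ from the true level by independent visit noise of SD e. The SD of the change is held at 7, so the SD of true change is √(49 − 2e²). The change is regressed on Day 1 ppFEV1 with and without the stratum. The cut in SE is 1 − √(1 − variance cut).

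| Visit noise SD e | SD of true change | Variance cut | SE cut |
|---|---|---|---|
| 1 | 6.86 | under 0.1% | under 0.1% |
| 2.5 | 6.04 | about 0.9% | about 0.5% |
| 3.5 | 4.95 | about 2.6% | about 1.3% |
| 4.95 | 0 | about 7% | about 3.7% |

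The last row is a limiting case: 4.95 × √2 = 7.0, so the whole planning SD is measurement noise and no subject truly changes. A separate grid with true-level SD 12 to 15 and noise SD 3 to 6 gave SE cuts of 1.3% to 4.0%.

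These scenarios treat screening and Day 1 as exchangeable readings. Adding an extra SD of 5 at screening, for bronchodilator state and Run-in changes, lowers the variance cut at e = 3.5 from about 2.6% to about 1.8%.

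**4. Mixed-model simulation.** Stratified 2:2:1:1 allocation, 10% dropout, 300 runs per scenario. Each cell shows the value without → with the stratum.

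| Contrast | Model SE, e = 4.95, no true change | Sampling SD | Model SE, e = 4.0, subject-level change SD 4.0 | Sampling SD |
|---|---|---|---|---|
| VX-371 + HS vs VX-371 + placebo | 1.185 → 1.142 | 1.169 → 1.152 | 1.195 → 1.174 | 1.170 → 1.165 |
| VX-371 + HS vs placebo | 1.183 → 1.140 | 1.131 → 1.113 | 1.195 → 1.173 | 1.139 → 1.137 |
| VX-371 + HS vs HS | 0.728 → 0.727 | 0.714 → 0.712 | 0.592 → 0.592 | 0.562 → 0.562 |

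For the two between-subject contrasts the reported SE falls by 1.8% to 3.6%, while the actual spread of the estimates falls by only 0.2% to 1.6%. For the VX-371 + placebo mean the model SE falls by 1.7% to 3.4%. The primary SE changes by about 0.1% or less.

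**The case against.** The strongest reply is that the stratifying variable is already in the model, measured later and kept continuous. Preferring a continuous measure to a cut-point is a defensible choice. This stands, and it is why the gain is small. A reader might infer that the analysis fails to follow the randomisation; the documents do not support that. What is missing is a dichotomised earlier reading of a covariate that the model keeps.

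A reader might also infer a real loss of precision. That is mostly unsupported too. Stratified allocation has already balanced the factor, so the estimates themselves barely become more stable. What changes is the reported SE, which is slightly conservative without the stratum.

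The correlation that reproduces the plan's 81% is zero, where there is no gain at all. That is a planning value, however. Both periods' changes are measured on the same subject from the same baseline, and Protocol 8.2.1 chose the crossover for its power, so some positive correlation is to be expected.

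The stakes are low. The saline sequences are there to give insight and inform later studies (Protocol 8.2.1), and enrolment in them may be stopped for administrative reasons (Protocol 8.1). Parts of SAP 9.3 are also redacted or not shown, so a sensitivity analysis using the stratum cannot be excluded. Neither point removes the gap in the stated model that produces these contrasts.

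Finally, entering screening ppFEV1 as a second continuous covariate might gain more. That is a different change and should not be counted as the benefit of this one.

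**Conclusion.** The point holds as a minor improvement. The 9.3.1.2 model omits the randomisation stratum without giving a reason. The effect is confined to the reported SEs of the two between-subject secondary contrasts and the within-treatment means, which are too large by somewhere between nothing and about 4%. The upper figure requires essentially all of the planning SD to be visit noise; at a noise SD of 2.5 to 3.5 the figure is about 0.5% to 1.3%. In power terms this is at most about 64% to 68% for an assumed 3-point between-subject difference.

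The size rests on assumed visit noise, true-level spread and within-subject correlation, none of which the documents give. No bias or inflated error rate is shown. The primary contrast is essentially unchanged, and the stated 80% within-treatment power reproduces without the stratum.

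**What to change.** Add the randomisation stratum (screening ppFEV1 <70 / ≥70, as used for allocation) as a fixed effect in the SAP 9.3.1.2 model, and keep study-baseline ppFEV1 as the continuous covariate. Say how the within-treatment LS means are weighted over the two strata, preferably by the observed stratum sizes, so that the new term does not shift what those means estimate.

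The cost is one model term and one between-subject degree of freedom among about 135 evaluable subjects (90 + 45). No new data are needed, because the stratum is already recorded and tabulated under SAP 9.2.1. The change can be made while the SAP is open, before database lock and unblinding. If the sponsor prefers the present model, one sentence giving the reason would be enough.

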### **9.3.4 Multiplicity Adjustment**

No multiplicity adjustment will be implemented.

## **9.4 Safety Analysis**

All safety analyses will be based on the set of data associated with the TE period for Treatment Period 1 and the TE period for Treatment Period 2. Safety analyses will use the Safety Set. Subjects will be analyzed according to the treatment they actually received in a given treatment period. For subjects receiving study drug from more than one treatment group in the same treatment period, the treatment group allocation will be determined using the following order: VX-371 + HS > VX-371 + Placebo > HS > Placebo. For safety analysis, the period baseline will be used.

All safety data will be presented in individual subject data listings.

The overall safety profile of inhaled study drug will be assessed in terms of the following safety and tolerability endpoints:

- Incidence of treatment-emergent adverse event (TEAEs)
- Clinical laboratory values (i.e., hematology, serum and plasma chemistry, coagulation studies, and urine studies)
- ECG results
- Vital signs
- Ophthalmologic examination results (for pediatric subjects <18 years of age only)
- Spirometry

Only descriptive analysis of the safety data will be performed; no statistical testing is planned.

### 9.4.1 Adverse Events

For analysis purposes, AEs will be classified as pretreatment AEs, TEAEs or post-treatment AEs, defined as follows:

**Pretreatment AE:** any AE that started before the start of inhaled study drug dosing in the study.

**TEAE:** any AE that increased in severity or that was newly developed during the TE period for Treatment Period 1 or Treatment Period 2. An AE that starts (or increases in severity) during a specific treatment period will be attributed to the inhaled study drug the subject was receiving during the treatment period.

**Post-treatment AE:** any AE that increased in severity or that was newly developed beyond the TE period for Treatment Period 2, or between the TE periods for Treatment Period 1 and Treatment Period 2, or beyond the TE period for Treatment Period 1 for subjects who do not have Treatment Period 2

For AEs with a missing or partially missing start date, if there is no clear evidence that the AE started (or increased in severity) before the first dose in Treatment Period 1, the start date will be imputed to the first dosing date in Treatment Period 1 and the AE will be assigned to the treatment in Treatment Period 1. For AEs with partially missing start date that indicates the AE started (or increased in severity) after the TE period of Treatment Period 1, but no clear evidence that it started before the first dose in Treatment Period 2, the start date will be imputed to the first dosing date in Treatment Period 2 and the AE will be assigned to the treatment in Treatment Period 2. Details for imputing missing or partial start date of AEs are described in Section [12.4](#).

#### 9.4.1.1 Over view of Treatment emergent AEs

An overview of all TEAEs will be summarized in the following categories:

- All TEAEs
- Grade 3/4 TEAEs
- TEAEs by relationship to study drug regimen
- TEAEs by relationship to study device
- TEAEs by maximum severity
- TEAEs leading to treatment interruption (this will include TEAEs leading to treatment interruption of inhaled study drug, Orkambi, and either inhaled study drug or Orkambi)
- TEAEs leading to treatment discontinuation (this will include TEAEs leading to discontinuation of inhaled study drug, Orkambi, and either inhaled study drug or Orkambi)
- Serious TEAEs
- Related serious TEAEs

- TEAEs leading to death

#### **9.4.1.2 TEAEs and TE SAEs by System Organ Class and Preferred Term**

The number and percentage of subjects with TEAEs will be summarized by treatment group, MedDRA system organ class (SOC) and preferred term (PT), where multiple occurrences of the same AE for the same subject will be counted only once. The summary table will be presented in descending order of frequencies in the VX-371 + HS treatment group. TE SAEs will be summarized similarly.

#### **9.4.1.3 TEAEs and TE SAEs by PT**

The number and percentage of subjects with TEAEs will be summarized by treatment group and PT, where multiple occurrences of the same AE for the same subject will be counted only once. TE SAEs will be summarized similarly.

#### **9.4.1.4 Related TEAEs and TE SAEs by SOC, PT**

The number and percentage of subjects with related TEAEs will be summarized by treatment group, SOC, and PT, where multiple occurrences of the same AE for the same subject will be counted only once. The summary table will be presented in descending order of frequencies in the VX-371 + HS treatment group. TEAEs in the following relationship to study drug regimen categories will be considered as related: Related, Possibly Related and Missing. TE SAEs will be summarized similarly.

In addition, related TEAEs pertaining to the study device will be summarized by treatment group and PT.

#### **9.4.1.5 Grade 3/4 TEAEs by SOC, PT**

The number and percentage of subjects with Grade 3/4 TEAEs will be summarized by treatment group, SOC, and PT, where multiple occurrences of the same AE for the same subject will be counted only once. The summary table will be presented in descending order of frequencies in the VX-371 + HS treatment group. Grade 3/4 TEAEs include severe and life-threatening adverse events.

#### **9.4.1.6 Respiratory Events and Symptoms**

Respiratory symptoms are defined as any TEAEs for the following 3 PTs:

- Chest discomfort
- Dyspnoea
- Respiration abnormal

Respiratory events are defined as any of the afore-mentioned respiratory symptoms, or any TEAEs for the following 4 additional PTs:

- Asthma
- Bronchial hyperreactivity
- Bronchospasm
- Wheezing

A summary of TE respiratory symptoms and events will be presented:

[figure not shown]
1. Showing number and percentage of subjects overall as well as by PT;
2. Showing number and percentage of subjects by maximum severity;
3. Summary of time-to-first onset (relative to first dose date of inhaled study drug in the treatment period)
4. Summary of duration of events (days) with descriptive summary;
5. Showing number and percentage of subjects with TEAE leading to treatment interruption of inhaled study drug, Orkambi, and either inhaled study drug or Orkambi; with TEAE leading to treatment discontinuation of inhaled study drug, Orkambi, and either inhaled study drug or Orkambi; with serious TEAEs; with related serious TEAEs; and with TEAE leading to death.

[figure not shown]
#### **9.4.1.7 Hyperkalaemia**

The following AE PTs will be selected for hyperkalaemia:

- Hyperkalaemia
- Blood potassium increased

A summary of hyperkalaemia will be presented using an approach similar to that for respiratory symptoms and events.

#### 9.4.2 Clinical Laboratory

For treatment emergent laboratory measurements, the raw values and change from period baseline values of the continuous laboratory continuous laboratory measurements (chemistry, hematology, and coagulation) will be summarized in SI units using descriptive statistics by treatment group at each scheduled time point. Urine sodium to potassium ratios will be summarized by treatment group.

The number and percentage of subjects with abnormal high (>ULN) hematology and chemistry values will be summarized by visit, as will the number and percentage of subjects with abnormal low (<LLN) hematology and chemistry values.

The number and percentage of subjects with laboratory measurements meeting the threshold analysis criteria during the TE period will be presented. The threshold analysis criteria are provided in Section 12.5 (Table 12-8 Threshold Criteria for Laboratory Tests).

The incidence of LFTs meeting the threshold analysis criteria during the TE period against the period baseline threshold criteria will also be summarized by treatment group (only worsening of the shift from period baseline will be presented).

Mean values ( $\pm$  SD) will be plotted against visit for plasma potassium, ALT, AST, alkaline phosphatase, GGT, and total bilirubin.

A listing of subjects with elevated liver function test (LFT, alanine aminotransferase [ALT]>3 Upper Limit Normal [ULN], aspartate aminotransferase [AST]>3 ULN, serum alkaline phosphatase [ALP]>1.5 ULN, direct bilirubin>1.5 ULN, and total bilirubin>1.5 ULN) results during the TE period will be presented. The listing will include all parameters of the LFT assessment at all visits.

A listing of subjects with elevated plasma potassium level at any time point during the TE period will be provided. The listing will include all plasma potassium measurements at all visits.

Results of urinalysis and serum pregnancy tests will be listed in individual subject data listings only. In addition, a listing containing individual subject laboratory measurements outside the reference ranges will be provided. This listing will include data from scheduled and unscheduled time points.

